#### 4.1.1. General Methodology

Participants who prematurely withdraw from study will not be replaced.

Unless specified otherwise, continuous data will be summarized using descriptive statistics: n, mean, standard deviation (std), median, minimum, and maximum. Categorical data will be summarized as the number and percentage of participants. No imputation of study data will be applied. Percentages will be presented as per GSK statistical display principles.

#### 4.1.2. Baseline and Change from Baseline Definition

##### Baseline definition: -

For all endpoints baseline value will be defined as per Table 1 and Table 2

**Table 1 Baseline Definition for Laboratory PD and Safety Parameters and Safety Endpoints**

	Baseline To be used in Analysis/Summaries			
	Period 1	Period 2	Period 3	Period 4
Laboratory PD and Safety parameters - Serum potassium (PD) and Glucose (safety) Safety endpoints - 12-lead ECG [1][2] Vital Signs	Predose Day 1	Predose Day 4	Predose Day 7	Predose Day 10

[1] Taken in triplicate.

[2] Mean of the triplicate 12-lead ECG measurement from the Day 1 assessment (pre-dose).

For safety endpoints, if a pre-dose observation of day i (where i = 1,4,7 and 10) is missing in a given period, then the day-1 or screening (latest available observation) value may be used as baseline.

**Table 2 Baseline Definition for Clinical Laboratory Assessment**

Parameter	Study Assessments Considered as Baseline		Baseline To be used in Analysis/Summaries
	Screening/Day -28 to -1	Day -1	
Clinical Laboratory Parameters			
Hematology	x	x	Day -1
Clinical chemistry	x	x	Day -1
Urinalysis	x	x	Day -1

If day -1 clinical laboratory assessment is missing for any endpoint, then latest data prior to day -1 (pre-dose) will be considered as baseline.

If either baseline or post-baseline data is missing, then change from baseline will be set to missing at that timepoint for all parameters.

Change from baseline definition: -

Change from baseline will be calculated as given follows: -

Change from baseline = Post-randomization assessment value – Baseline assessment value at each dosing period.

## 4.2. Primary Endpoint(s) Analyses

Primary estimands (refer Section 1.1) for primary endpoints will be implemented for the primary analysis.

### 4.2.1. Definition of primary endpoints

The Primary endpoints are defined in Section 1.1.

The definitions of primary PK parameters are described in [Table 3](#).

**Table 3 Primary Pharmacokinetic Parameters**

PK Parameters	Descriptions
AUC(0-30min)	Area under the plasma concentration-time curve up to 30 minutes postdose and trapezoidal methods will be used to calculate it.
AUC(0-∞)	Area under the plasma concentration-time curve from time 0 to infinity calculated as: $AUC(0-∞) = AUC(0-\text{last}) + C(\text{last})/k(\text{el})$ , where $C_{\text{last}}$ is the last measurable plasma concentration and $K(\text{el})$ is the elimination rate constant.
Cmax	Maximum observed plasma concentration

#### 4.2.2. Main analytical approach

The primary pharmacokinetic (PK) endpoints will be analyzed for Cohort 1 and Cohort 2 using PK analysis set.

For the  $\log_e$  transformed data of AUC(0-30min), AUC(0- $\infty$ ) and Cmax, descriptive statistics (N, n, GM, 95% CI of GM, SD ( $\log_e$ ), between- subject coefficient of variation (CVb in %)) will be presented, where  $\%CV_b=100*(SQRT(EXP(SD^2)-1))$  and SD is the standard deviation on the  $\log_e$  scale.

For the untransformed data of AUC(0-30min), AUC(0- $\infty$ ) and Cmax, descriptive statistics (N, n, AM, 95% CI of AM, SD ) median, minimum and maximum) will be computed.

AUC (0- $\infty$ ) will be reported with <20% of AUC(0-inf) of this area coming from extrapolation. It will be acceptable to include data from profiles with >20% extrapolated if at least 80% of the profiles in the study have <20% of the of the AUC(0-inf) as extrapolated area. It will be unacceptable to use AUC(0-inf) data if >40% of the AUC has been extrapolated, except in specific situations which will be justified in the study report.

##### Statistical model for the analysis of primary PK parameters - AUC(0-30min), AUC(0- $\infty$ ) and Cmax

For each cohort, following  $\log_e$ -transformation, AUC(0-30min.), AUC(0- $\infty$ ) and Cmax will be separately analyzed using mixed effect model approach with fixed effect terms for sequence, period and treatment group. Participants will be treated as random effects in the model. Factor analytic (FA(02))variance and covariance structures will be assumed. If the above model fails to converge, other covariance structures (e.g., UN, CS, AR (1), VC etc.) might be investigated. The point estimates and their associated 90% CI will then be back-transformed to provide point estimates and 90% CI for the ratios (GMR) of HFA-152a MDI (test)/HFA-134a MDI (reference).

If an intercurrent event (ICE) (as described in Section 1.1) happens during a specific treatment period, and this event affects the measurement of individual pharmacokinetic (PK) concentrations (pharmacokinetic data), then the data points for those affected individuals in the treatment period will be set to missing.

[figure not shown]
##### Criteria Necessary to Declare Average Bioequivalence (ABE)

If for the reference product,  $S_{WR}<0.294$  or  $C_{WR}<30\%$ , then ABE approach will be used for the acceptance range limit of BE (refer [Table 4](#)).

**CONFIDENTIAL**

219728

CCI

CCI

CCI

## 4.3. Secondary Endpoint(s) Analyses

Secondary PK endpoints will be analyzed using the secondary estimands (refer to Section 4.3.1.1). Secondary safety endpoints will be analyzed considering safety estimand (refer to Section 4.3.1.1).

### 4.3.1. Secondary endpoints

The secondary endpoints are defined in Section 1.1.

The definitions of secondary PK parameters are described in Table 5.

**Table 5 Secondary Pharmacokinetic Parameters**

PK Parameters	Descriptions
Tmax	Time to Cmax
t1/2	Apparent terminal phase half-life
AUC(0-last)	Area under the plasma concentration-time curve up to last time with concentrations above the LLOQ. AUC(0-last) is calculated by a combination of linear and logarithmic trapezoidal methods.

#### 4.3.1.1. Definition of estimands

##### Estimand for Pharmacokinetic (PK)

Cohort 1:

Test: Salbutamol HFA-152a MDI 200 µg

Reference: Salbutamol HFA-134a MDI 200 µg

The secondary clinical question of interest for Cohort 1 is:

What is the summarized PK profile in Cohort 1 using descriptive statistics for Tmax and t1/2 and GMR for AUC(0-last) between salbutamol HFA-152a and salbutamol HFA-134a in healthy participants after administration of single dose of 200  $\mu\text{g}$ ?

The secondary estimand for Cohort 1 has the same estimand attributes as the primary estimand (refer Section 1.1) for Cohort 1 (population, treatment condition, ICE strategy), except for the estimand attributes of PK endpoints and population-level summary measure:

- The secondary PK parameters endpoints are Tmax, t1/2, AUC(0-last).
- The population level summaries to be estimated are:
  - AM with 95% CI for Tmax and GM with 95% CI for t1/2.
  - Ratio of adjusted GM (for logarithmic transformed values) of 2 formulations (test/reference) with 90% CI for AUC(0-last).

Cohort 2:

Test: Salbutamol HFA-152a MDI 800  $\mu\text{g}$

Reference: Salbutamol HFA-134a MDI 800  $\mu\text{g}$

The secondary clinical question of interest for Cohort 2 is -

What is the summarized PK profile in Cohort 2 using descriptive statistics for Tmax and t1/2 and GMR for AUC(0-last) between salbutamol HFA-152a and salbutamol HFA-134a in healthy participants after administration of single dose of 800  $\mu\text{g}$ ?

The secondary estimand for Cohort 2 has the same estimand attributes as the primary estimand (refer Section 1.1) for Cohort 2 (population, treatment condition, ICE strategy), except for the estimand attributes of PK endpoints and population-level summary measure:

- The secondary PK parameters endpoints are Tmax, t1/2, AUC(0-last).
- The population level summaries to be estimated are:
  - AM with 95% CI for Tmax and GM with 95% CI for t1/2.
  - Ratio of adjusted GM (for logarithmic transformed values) of 2 formulations (test/reference) with 90% CI for AUC(0-last).

**Estimand for Intra-participant variability of pharmacokinetic (PK) parameters**

Cohort 1:

Test: Salbutamol HFA-152a 200  $\mu\text{g}$

Reference: Salbutamol HFA-134a 200  $\mu\text{g}$

The secondary clinical question of interest for Cohort 1 is -

What is the intra-participant variability of the PK profile of Cohort 1 using  $CV_{WR}$  for AUC (0-30min), AUC (0- $\infty$ ), Cmax and AUC (0-last) PK parameters for salbutamol HFA-152a and salbutamol HFA-134a in healthy participants after administration of a single dose of 200  $\mu$ g?

This secondary objective is to establish whether either the reference or test product is considered a high variable product at the 200  $\mu$ g dose level ( $CV_{WR}>30\%$ ).

The secondary estimand for Cohort 1 has the same estimand attributes as the primary estimand for Cohort 1 (population, treatment condition, ICE strategy), except for the estimand attributes of PK endpoints and population-level summary measure:

- The secondary PK parameters endpoints for HFA-152a (test) and HFA-134a (reference) are:
  - Intra-participants variability in AUC(0-30min)
  - Intra-participants variability in AUC(0- $\infty$ )
  - Intra-participants variability in Cmax
  - Intra-participants variability in AUC(0-last)
- The population level summaries to be estimated for HFA-152a (test) and HFA-134a (reference) are:
  - Intra(within)- participants  $CV_{WR}$  (%) for AUC(0-30min), AUC(0- $\infty$ ), Cmax and AUC(0-last)

#### Cohort 2:

Test: Salbutamol HFA-152a 800  $\mu$ g

Reference: Salbutamol HFA-134a 800  $\mu$ g

The secondary clinical question of interest for Cohort 2 is -

What is the intra-participant variability in PK profile of Cohort 2 using  $CV_{WR}$  for AUC(0-30min), AUC(0- $\infty$ ), Cmax and AUC(0-last) PK parameters for salbutamol HFA-152a and salbutamol HFA-134a in healthy participants after administration of single dose of 800  $\mu$ g?

This secondary objective is to establish whether either the reference or test product is considered a high variable product at the 800  $\mu$ g dose level ( $CV_{WR}>30\%$ ).

The secondary estimand for Cohort 2 has the same estimand attributes as the primary estimand for Cohort 2 (population, treatment condition, ICE strategy), except for the estimand attributes of PK endpoints and population-level summary measure:

- The secondary PK parameters endpoints for HFA-152a (test) and HFA-134a (reference) are:
  - Intra-participants variability in AUC(0-30min)

- Intra-participants variability in AUC(0-∞)
- Intra-participants variability in Cmax
- Intra-participants variability in AUC(0-last)
- The population level summaries to be estimated for HFA-152a (test) and HFA-134a (reference) are:
  - Intra(with-in)- participants CVWR (%) for AUC(0-30min), AUC(0-∞), Cmax and AUC(0-last)

Rationale for supporting secondary estimands of PK parameters for both cohorts:

Rational for supporting secondary estimands of PK parameters for both cohorts is the same as primary estimands (refer Section 1.1).

### Estimands for Safety

#### Cohort 1:

Test: Salbutamol HFA-152a MDI 200 μg

Reference: Salbutamol HFA-134a MDI 200 μg

The clinical question of interest for the safety secondary objective in Cohort 1 is -

What is the safety and tolerability profile of single doses 200 μg of salbutamol in Cohort 1 healthy participants delivered via MDIs?

The secondary safety estimand for Cohort 1 is described by the following attributes:

- The population is healthy male or female participants aged 18 to 55 years.
- The secondary safety endpoints are:
  - Incidence of AEs and SAEs
  - Absolute values for 12-lead ECGs recording of HR and QTc intervals at each assessed visit
  - Change from baseline for postdose 12-lead ECGs recording of HR and QTc intervals at each assessed visit
  - Absolute values of clinical laboratory parameters at each assessed visit
  - Absolute values of vital signs (systolic and diastolic blood pressure and pulse rate) at each assessed visit.
- Treatment condition is administration of salbutamol as a single 200 μg dose, given as 2 actuations each separated by a 20-second interval, each delivering 100 μg of salbutamol (as salbutamol sulfate) as the ex-valve dose for the HFA-152a MDI or HFA-134a MDI.
- The ICEs and estimand strategies are as follows:

- Study treatment discontinuation due to any reason (treatment policy strategy). Interest lies in the group of participants irrespective of whether they completed the study intervention.
- Occurrence of emesis or coughing on dosing (treatment policy strategy).
- Dosing error: Considered less than or more than prescribed dose (treatment policy strategy).
- Use of prohibited or rescue medication which impacts the PK parameters (Treatment policy strategy).
- The population level summaries to be estimated are:
  - Number and percentages for incidence of AEs and SAEs
  - Mean of absolute values for 12-lead ECGs recording of HR and QTc intervals at each assessed visit
  - Mean of change from baseline values for postdose 12-lead ECGs recording of HR and QTc intervals at each assessed visit
  - Mean of absolute of clinical laboratory parameters including vital signs (systolic and diastolic blood pressure and pulse rate) at each assessed visit

Cohort 2:

Test: Salbutamol HFA-152a MDI 800  $\mu$ g

Reference: Salbutamol HFA-134a MDI 800  $\mu$ g

The clinical question of interest for the safety secondary objective in Cohort 2 is -

What is the safety and tolerability profile of single doses 800  $\mu$ g of salbutamol in Cohort 2 healthy participants delivered via MDIs?

The secondary safety estimand for Cohort 2 has the same estimand attributes as Cohort 1 (population, PK endpoints, population-level summary measure, ICE strategy), except for the attribute for the treatment condition:

- Treatment condition is administration of salbutamol as a single 800  $\mu$ g dose, given as 8 actuations each separated by a 20-second interval, each delivering 100  $\mu$ g of salbutamol (as salbutamol sulfate) as the ex-valve dose for the HFA-152a MDI or HFA-134a MDI.

Rationale for estimands supporting secondary safety objectives in both cohorts: This is a study in healthy volunteers with short follow-up duration. Therefore, all AEs, SAEs, 12 lead ECGs, laboratory parameters and vital signs data are of interest, regardless of ICES to support completeness of reporting and transparency of the clinical study.

Counts and Percentages will be presented for intercurrent events for primary and secondary endpoints.

#### 4.3.1.2. Main analytical approach

The secondary pharmacokinetic (PK) endpoints will be analyzed for Cohort 1 and Cohort 2 using PK analysis set.

For the  $\log_e$  transformed data of t1/2 and AUC(0-last), descriptive statistics (N, n, GM, 95% CI of GM, SD ( $\log_e$ ), between- subject coefficient of variation (CVb in %)) will be presented, where  $\%CV_b=100*(\text{SQRT } (\text{EXP}(\text{SD}^2)-1))$  and SD is the standard deviation on the  $\log_e$  scale.

For the untransformed data of Tmax, t1/2 and AUC(0-last), descriptive statistics (N, n, AM, 95% CI of AM, SD, median, minimum, and maximum) will be presented. All PK parameters will be summarized by study treatment.

##### Statistical model for the analysis of secondary PK endpoint - AUC(0-last)

For each cohort, following  $\log_e$ -transformation, AUC(0-last) will be analyzed using a mixed effect model approach with fixed effect for sequence, period, treatment group and participants as random effects. Factor Analytic (FA(02)) variance and covariance structures will be assumed. If the above model fails to converge, other covariance structures (e.g. UN, CS, AR (1), VC etc.) might be investigated. The point estimates and their associated 90% CI will then be back-transformed to provide point estimates and 90% CI for the ratios (GMR) of HFA-152a MDI (test)/HFA-134a MDI (reference).

##### Statistical model for estimating the intra-participants (with-in) variability for PK parameters – AUC (0-30min), AUC (0-∞), Cmax and AUC (0-last)

For each cohort, following  $\log_e$ -transformation, AUC (0-30min.), AUC (0-∞), Cmax and AUC (0-last) will be analyzed using a mixed effect model approach with fixed for period, treatment group and participants as random effects. Factor Analytic (FA(02)) variance and covariance structures will be assumed. If the above model fails to converge, other covariance structures (e.g. UN, CS, AR (1), VC etc.) might be investigated. SD in  $\log_e$  scale and coefficient of variation (CVWR) for intra (within)-participants will be computed, where  $\%CV_{WR}=100*(\text{SQRT } (\text{EXP}(\sigma_{WR}^2)-1))$  and  $\sigma_{WR}^2$  is the mean squares error (MSE) or residual in  $\log_e$  scale from the statistical mixed model.

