9.3.1.2. Main Analytical Approach

The primary analysis for PK parameters AUC(0-30min), AUC(0-∞) and Cmax will evaluate the primary estimand in PK analysis set.

If for the reference product, $SD_{WR} < 0.294$ or $CV_w < 30\%$, then ABE approached will be used, refer [Section 10.8, Table 12](#) for the acceptance range limit of BE.

If for the reference product, $SD_{WR} \geq 0.294$ or $CV_w \geq 30\%$, then RSABE approached will be used, refer [Section 10.8, Table 12](#) for the acceptance range limit of BE.

The extent of the widening is defined based upon the within-subject variability seen in the bioequivalence study using scaled-average-bioequivalence according to $[U, L] = \exp[\pm k \cdot Sw_r]$, where U is the upper limit of the acceptance range, L is the lower limit of the acceptance range, k is the regulatory constant set to 0.760 as per EMA and 0.893 according to FDA and Sw_r is the within-subject standard deviation of the log-transformed values of Cmax and AUC of the reference product (refer [Section 10.8, Table 12](#)).

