9.3.1.4. Secondary endpoint(s) analyses

The secondary analysis for PK parameters AUC(0-30min), AUC(0-∞) and Cmax will evaluate the secondary estimand in PK analysis set.

In each cohort, analytical approach for the statistical analysis of AUC(0-last) is same as primary PK parameters as mentioned in Section 9.3.1.2.

Statistical model for estimating the intra-participants (within) variability.

For each cohort, following log_e-transformation, AUC(0-30min.), AUC(0-∞), Cmax and AUC(0-last) will be analyzed using mixed effect model approach with fixed for period, treatment group and participants as random effects. SD in log scale and coefficient of variation (CV_{WR}) for intra (within)-participants will be computed.

Statistical model for estimating the inter-participants (intra participants for test and reference) variability.

For each cohort, following log_e-transformation, AUC(0-30min.), AUC(0-∞), Cmax and AUC(0-last) will be analyzed using mixed effect model approach with fixed for period, treatment group and treatment group as random effects. SD in log scale and coefficient of variance (CV) for inter-participants will be calculated.

- Total participants variability will be calculated as sum of intra (within)-participants and inter-participants variability.

If an intercurrent events (ICEs) (as described in Section 3.2.1 and Section 3.2.2) happens during a specific treatment period, and this event affects the measurement of individual pharmacokinetic (PK) concentrations (pharmacokinetic data), then the data points for those affected individuals in the treatment period will be set to missing.

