9.5. Sample size determination

Up to 60 healthy participants will be enrolled to either Cohort 1 (200 µg) or Cohort 2 (800 µg) to achieve at least 56 participants in the PK analysis set.

For each cohort, 30 healthy participants will be randomly assigned to a cohort to ensure at least 28 participants are included in the PK analysis set with 15 randomized to each treatment sequence.

The target number of participants in each cohort is chosen to achieve half width (refer [Table 9](#)) of the 90% CI, in the estimate of the geometric mean ratios for the primary endpoints (AUC (0-30 min.), AUC(0-inf) and Cmax).

In the previously conducted 219430 pilot PK study, there was considerable interest in AUC(0-30 min) due to larger than expected observed differences between test and reference product, in addition to observing potentially higher amounts of intra-subject variability that would classify the product as highly variable (~30%). Though, less variability was observed among AUC(0-inf) and Cmax. Due to uncertainty of what the true CVw may be for both the reference and test products, this current study therefore has considered a more conservative assumption accounting for up to 50% intra subject variability (CVw) in PK parameters, with a particular interest in AUC(0-30 min).

Therefore, a sample size 28 in each cohort, assuming intra subject variability (CVw) of 50% in AUC(0-30 min.), the half width of the upper bound of the 90% CI for observed GMR (T/R) is 16.44% (refer [Table 9](#)).

For example, if the geometric ratio between test and reference is 1.06 for n=28 and CVw = 50%, then the upper bound of the 90% CI for observed treatment ratio is $1.06 * (1 + 0.1644) = 1.23$ and the lower bound is $1.06 / (1 + 0.1644) = 0.91$ (refer [Table 10](#)).

Table 9 Sample sizes with varying intra subject variability and associated half-widths of the 90% CI of the observed treatment ratio

CCI

CCI

Table 10 Sensitivity Table

CCI

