##### Statistical model for estimating the inter-participants (intra participants for test and reference) variability for PK parameters – AUC (0-30min), AUC (0-∞), Cmax and AUC (0-last)

For each cohort, following  $\log_e$ -transformation, AUC (0-30min.), AUC (0-∞), Cmax and AUC (0-last) will be analyzed using a mixed effect model approach with fixed for period, treatment group and treatment group as random effects. Factor Analytic (FA(02)) variance and covariance structures will be assumed. If the above model fails to converge, other covariance structures (e.g. UN, CS, AR(1), VC etc.) might be investigated. SD in  $\log_e$  scale and coefficient of variance (CV) for inter-participants will be calculated.

- Total participants variability will be calculated as the sum of intra (within)- participants and inter-participants variability.

If an intercurrent events (ICEs) (as described in Section 4.3.1.1 - intra-participants variability of PK parameters) happens during a specific treatment period, and this event affects the measurement of individual pharmacokinetic (PK) concentrations (pharmacokinetic data), then the data points for those affected individuals in the treatment period will be set to missing.

Graphs for Pharmacokinetic (PK) parameters -

- Individual plasma concentration - time plots (linear and semi-logarithmic) by subjects
- Individual plasma concentration - time plots (linear and semi-logarithmic) by treatment group
- Median (range) plasma concentration - time plot (linear and semi-logarithmic) by treatment group
- Mean ( $\pm$  SD) plasma concentration - time plots (linear and semi-logarithmic) by treatment group
- Mean ( $\pm$  SD) plasma concentration - time plots (linear and semi-logarithmic)

To present the descriptive statistics and plots for PK parameters, refer the GSK statistical analysis SOPs.

Listing for PK concentration and PK parameters (AUC(0-30min), AUC(0- $\infty$ ), Cmax, Tmax, t1/2 and AUC(0-last)) will be generated using PK analysis set.

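### The SAP sets the within-participant CV equal to one residual pooled over test and reference, so it is not the reference variance and cannot give the two product-specific CVs that the secondary endpoint requires

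*SAP*

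**What the plan says.** The secondary endpoints (Protocol Section 3, Table 3; SAP 1.1) list within-participant variability of AUC(0-30min), AUC(0-∞), AUC(0-last) and Cmax separately for HFA-152a and for HFA-134a. SAP 4.3.1.1 gives the purpose: "to establish whether either the reference or test product is considered a high variable product", judged at 30% in each cohort. It labels the summary CV_WR for both products.

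SAP 4.3.1.2 supplies the estimator. Each log-transformed parameter goes into one mixed model per cohort, with period and treatment fixed and participants random, under an FA(02) structure. The SAP then states that σ²_WR "is the mean squares error (MSE) or residual in" the log scale, and converts it to a CV by 100·√(exp(σ²_WR) − 1). It mentions neither a reference-only fit nor a residual that differs by treatment. Protocol 9.3.1.4 uses the same model: a "mixed effect model approach with fixed for period, treatment group and participants as random effects".

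A second model in SAP 4.3.1.2 has a heading that refers in brackets to intra-participant variability for test and reference. Its text reads "fixed for period, treatment group and treatment group as random effects", and its stated output is that the "coefficient of variance (CV) for inter-participants will be calculated".

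Protocol 9.3.1.2 defines the scaling SD differently: Sw_r "is the within-subject standard deviation of the log-transformed values of Cmax and AUC of the reference product". That SD drives the 0.294 / 30% switch and the limits exp(±k·Sw_r), with k = 0.760 (EMA) or 0.893 (FDA).

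**The concern.** Treatment is a fixed effect in the model, so both products contribute to its one residual. A single residual cannot describe two products, and it is not the reference variance that the subscript WR suggests. Followed as written, the secondary objective would be answered with one averaged number. A low-variability reference could be called highly variable because the test product is, or the reverse.

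A second, conditional consequence follows. If this σ_WR were also used for the choice between ABE and RSABE and for the widened limits, those would rest on the wrong variance.

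**Working it through.** **The plan's own figure.** Protocol 9.5 and SAP Section 5 give a 90% CI half-width of 16.44% at n = 28 and CVw = 50%.
- s = √ln(1 + 0.50²) = 0.4724
- SE = 0.4724/√28 = 0.0893
- exp(t₀.₉₅,₂₆ × SE) − 1 = exp(1.7056 × 0.0893) − 1 = 16.45%

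The figure reproduces to within rounding. It uses one common CV, so it neither depends on the present point nor tests it.

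**What the residual estimates.** Each participant receives T twice and R twice, so a single residual has expectation (s²_WT + s²_WR)/2. If the random effect is only a participant intercept, it also absorbs about one third of any participant-by-treatment variance. If FA(02) means treatment within participant, that extra term goes but the averaging stays, unless the residual is split by treatment.

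**Size.** The documents give no separate test and reference CVs, only about 30% and up to 50%, so every pair below is an assumption. With s² = ln(1 + CV²):
- R 25%, T 40%: (0.0606 + 0.1484)/2 = 0.1045, so s = 0.323 and CV = 33.2%. The reference s is 0.246.
- R 35%, T 20%: (0.1156 + 0.0392)/2 = 0.0774, so s = 0.278 and CV = 28.4%. The reference s is 0.340.
- R 25%, T 35%: (0.0606 + 0.1156)/2 = 0.0881, so s = 0.297 and CV = 30.3%.

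**Chance of reaching s ≥ 0.294.** The design is n = 28, with 14 per sequence. The single value was simulated with at least 20,000 trials per pair. Its range covers the intercept-only residual (80 df) and the average of the two product variances. The product-specific estimates come from differences between replicates within sequence (26 df each), so their chance is P(χ²₂₆ ≥ 26 × 0.294²/s²). For the reference at 25% this is P(χ²₂₆ ≥ 37.1) = 7%.

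| Assumed CV, R / T | Single SAP value | Reference only | Test only |
|---|---|---|---|
| 25 / 40 | 79–85% | 7% | 95% |
| 35 / 20 | 24–28% | 82% | 0% |
| 25 / 35 | 51–52% | 7% | 82% |
| 25 / 30 | 14–18% | 7% | 46% |
| 30 / 35 | 76–81% | 46% | 82% |
| 35 / 30 | 75–81% | 82% | 46% |
| 30 / 30 | 46–47% | 46% | 46% |
| 50 / 50 | about 100% | about 100% | about 100% |

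**Participant-by-treatment variance, intercept-only reading.** Take both CVs at 25% and an SD of 0.15 for the true T − R difference between participants. The expected residual is about 0.0606 + 0.15²/3 = 0.0681 (simulated mean 0.0680), a CV of 26.5% instead of 25%.

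**Limits, only if this residual feeds them.** At R 25 / T 40, exp(±0.893 × 0.3233) = 0.749 to 1.335 and exp(±0.760 × 0.3233) = 0.782 to 1.279. The reference SD of 0.246 is below the switch, so no widening would be due.

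**The case against.** The best reply is that this is loose notation and incomplete specification, not a decision to report an average. The SAP often uses CV_WR where the protocol has CVw. The estimand names each product, SAP 4.3.1.2 says PK parameters are summarised by treatment, and the heading of the second model suggests that treatment-specific within-participant variances were intended. FA(02) also makes little sense for a lone intercept, so the intercept-only reading may not be meant. All visible text ties the switch to the reference product, and Table 4 and SAP 6.5, where S_WR may be properly defined, are redacted. The illustrative pairs straddle 30%. The endpoint is descriptive.

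Much of this stands as a limit on the consequences. The effect on the BE limits is conditional, and the interaction term may not apply. Nothing visible shows that the products differ in variability, and where both CVs lie well to one side of 30% the classification hardly changes.

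It does not remove the defect. The SAP does more than leave a gap: it states a rule, and that rule gives one pooled value on either reading of the random effects. The second model does not repair it, because treatment is both fixed and random, no participant term is named, and only an inter-participant CV is output. Nor can equal variability be assumed. Protocol 9.5 explains its cautious 50% with the words "Due to uncertainty of what the true CVw may be for both the reference and test products", and puts the pilot value for AUC(0-30min) near 30%, where the classification is most sensitive.

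**Conclusion.** The concern holds, with high confidence, for the secondary variability endpoint. As written, SAP 4.3.1.2 estimates the average of two variances and calls it σ²_WR, so it cannot classify each product against 30%. The error is material when the products differ in variability and the threshold lies between or near their CVs. It vanishes in expectation when the CVs are equal and no participant-by-treatment variance enters the residual. The sizes rest on assumed CV pairs.

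The GMR, its 90% CI and the 16.44% half-width are not affected. An effect on the ABE/RSABE switch or the scaled limits is possible but cannot be judged from the visible text. If the redacted section defines S_WR from reference data alone, the SAP holds two definitions of one quantity, which also need reconciling. This should be fixed, but it does not threaten the primary comparison.

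**What to change.** - In SAP 4.3.1.2, specify treatment-within-participant random effects, where a two-factor structure has a role, with a separate residual variance for each treatment. Separate reference-only and test-only fits would also serve.
- Report CV_WR for the reference and CV_WT for the test product, and use these symbols consistently in 4.3.1.1 and 4.3.1.2.
- In the second variability model, correct the random effect and make the stated output match the heading.
- State that S_WR for the 0.294 switch and the widened limits is the reference-only estimate, and confirm that SAP 6.5 agrees.
- Align the model sentence in Protocol 9.3.1.4.

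The cost is SAP wording and one model option, the residual grouped by treatment. The replicate design already supports both CVs, so no extra participants or data are needed. Changing the protocol sentence would need an amendment, which could be combined with the next one.
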